2.4. Statistical Methods

2.4.1. General Overview and Plan of Analysis

All data will be analyzed using Statistical Analysis System (SAS Version 9.4 or higher for Windows, SAS Institute, Cary, NC). Continuous variables will be summarized using number, mean, standard deviation, median, minimum, and maximum. Categorical variables will be summarized using frequencies and percentages.

2.4.2. Hypothesis Testing

No formal hypothesis tests are planned.

2.4.3. Modeling

Not Applicable in this study.

2.4.4. Multiplicity Issues/Multiple Comparisons

There is no planned Multiplicity Issues/Multiple Comparisons analysis for this study.

2.4.6. Interim Analysis

No formal interim analysis is planned. AE listings and appropriate summary tables will be generated for Scientific Review Committee meetings and Development Safety Update Reports (DSURs).

2.4.7. Pharmacokinetic and Pharmacodynamic Analyses

Pharmacokinetic and Pharmacodynamic data will be summarized in a separate report.

3. Statistical Analysis

Data will be presented for clinical review and interpretation. Categorical variables will be summarized using frequency counts and percentages. Continuous variables will be summarized using descriptive statistics (n, mean, SD, median, minimum, and maximum). All listings will be presented for the FAS population except for PK and PD data.

3.1. Enrollment and Disposition of Subjects

Enrolled individuals are referred to as “subjects”. Subjects with acute myelogenous leukemia (AML), myelodysplastic syndrome (MDS), and chronic myelomonocytic leukemia (CMML) will be included.

Major selection criteria are: age \geq 18 years, confirmed high risk MDS/CMML or AML with documented disease progression following previous therapy, or subjects with AML \geq 60 years of age who are not candidates for other therapies. Subjects must be \geq 3 weeks beyond chemotherapy, radiotherapy, major surgery, or other experimental treatments, and recovered from all acute toxicities (\leq Grade 1), have adequate renal and hepatic function, and no known history of significant cardiac disease.

The analyses of subject disposition will be performed on the FAS population for subjects in Phase 1 dose escalation phase by dose cohort and for subjects in Phase 2a phase by MDS/CMML disease cohort. The number and percentage of subjects will be presented. The number of subjects treated, and treated subjects who completed follow-up and those who terminated early from treatment and the study, along with their reasons for early termination, will be presented.

3.2. Baseline Characteristics

3.2.1. Demographic

Summary statistics for demographic characteristics will be presented for subjects in Phase 1 dose escalation phase by dose cohort and for subjects in Phase 2a phase by MDS/CMML disease cohort using the full analysis set (FAS) population. Tabulations will be performed for age, sex (male or female), ethnicity (Hispanic/Latino or other), and race (American Indian or Alaska Native, Black or African American, White, Asian, Native Hawaiian or Other Pacific Islander, Unknown, or other). Age will be calculated as the number of complete years between a subject’s date of birth and the date of screening visit.

3.2.2. Physical Characteristics

Summary statistics will be presented for height (cm) and weight (kg) at screening for subjects in phase 1 by dose cohort and for subjects in phase 2a by disease cohort treated at RP2D using the FAS population. ECOG performance status at screening will be summarized.

3.2.3. Disease Characteristics

The baseline disease assessment (AML and MDS/CMML) will be summarized for phase 1 subjects by dose cohort and for phase 2a subjects treated at RP2D and schedule using the FAS population.

3.2.4. Concomitant Medications at Entry

Concomitant medications coded using WHO Drug Dictionary will be summarized using descriptive statistics for phase 1 subjects by dose cohort and for phase 2a subjects by MDS/CMML disease cohort using the FAS population. Medication start and stop dates will be compared to the date of first dose of medication to allow medications to be classified as either Prior or Concomitant. Medications that start and stop prior to the date of first dose of study medication will be classified as Prior medications. If a medication starts before the date of first dose of study medication or starts on or after the first dose of study medication, and

stops on or after the date of first dose of study medication, then the medication will be classified as Concomitant.

3.3. Analysis of Efficacy

All efficacy analyses will be conducted for Phase 1 subjects by dose cohort, if applicable, and for Phase 2a subjects by MDS/CMMML disease cohort at the RP2D and schedule (400 mg/m² BID x 21 days, repeated every 28 days) using the Per Protocol Population (PPS dataset).

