4.3. Discontinuation of Subjects

4.3.1. Procedures for Withdrawal

Any subject may be removed from study for the following reasons:

- Subject withdrawal of the informed consent
- Subject noncompliance
- An increasing or unexpected pattern of unacceptable toxicity
- Disease progression
- Investigator judgment when the well-being and best interest of the subject is compromised

Subjects experiencing unacceptable toxicity should be removed from the study once complete resolution of toxicity has been documented. Individual subjects may be discontinued from the study by the investigator or sponsor at any time if either determines that it is not in the best interest of the subject to continue.

Any subject who becomes pregnant during the study must be discontinued from the study immediately, but should be followed through delivery or termination of the pregnancy. Subjects should also notify the investigator if they become pregnant within 28 days following the last dose of study drug. FPHU/Westat also must be notified if a subject becomes pregnant on study.

If a subject is discontinued from the study before completing the specified duration of treatment, they should be encouraged to complete the end-of-study assessments and to agree to report any serious adverse events for 28 days following the last dose of study drug. The date the subject is withdrawn and the primary reason for discontinuation will be recorded on the case report form (CRF).

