7.2.4. Timing of Assessments to Determine Response

Disease assessments will be made at the end of Cycle 1 and Cycle 3 and every two cycles thereafter. Disease assessments may be made at other time points at the discretion of the Investigator.

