8.2. Analysis Populations

The full analysis set (FAS) includes all subjects who are administered any fraction of a dose of study medication. For a particular measure, the per-protocol set (PPS) includes those subjects in the FAS who have a valid baseline and one or more post-treatment assessments for that measure of interest.

The FF-10501-01 PK population consists of all subjects in the FAS who complete all PK assessments.

The FF-10501-01 PD population consists of all subjects in the FAS who complete all PD assessments.

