8.3.2.1. Primary Efficacy Endpoint

The primary efficacy endpoint is the proportion of subjects treated at the MTD in each disease cohort (AML, MDS or CMML) with objective response (OR) within 3 cycles of study drug (i.e., within 3 months). For subjects with AML, OR is CR, CRi, or PR, as defined above. For subjects with MDS or CMML, OR is CR, PR or marrow CR, as defined above. The proportion of subjects in each disease cohort treated at the MTD will be summarized, and 90% confidence intervals will be estimated.

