Appendix D. Schedule of Study Procedures

Study Activity	Screening ^a	Treatment Cycle 1					Treatment Cycles after Cycle 1		Progression or Relapse	End of Study ^o	Long-Term Follow-Up ^p
		Day 1	Day 8 ^k	Day 15 ^k	Day 22 ^k	End of Cycle 1 ^l	Day 1 ^m	End of Cycle 3 ⁿ			
Signed ICD	X										
Medical history	X										
Physical examination	X	X ^j					X ^j			X	
Vital Signs	X	X	X	X	X		X			X	
ECOG Performance Status	X	X					X			X	
Height	X										
Weight	X	X					X			X	
Hematology ^b	X	X	X	X	X		X			X	
Serum chemistry ^c	X	X	X	X	X		X			X	
Urinalysis ^d	X	X					X			X	
Beta-hCG for WCBP	X										
12-lead ECG	X	X ^e		X ^e			X ^e			X	
Concomitant medications	X						Continuous				
Adverse Event assessment							Continuous				
Bone Marrow Aspirate ^f	X					X		X	X		
Disease Response Assessment ^g	X					X		X	X		
Peripheral blood for PK assessment ^h		X		X							
Peripheral blood for PD (XMP) assessment ^h		X		X							
Administration of FF-10501-01 ⁱ		BID x 21 days					BID x 21 days				
Assessment of survival		X	X	X	X	X	X	X	X	X	X

^a Screening to be performed within 28 days of Cycle 1, Day 1

^b Hematology collected at Screening, Days 1, 8, 15 and 22 of Cycle 1, Day 1 of each subsequent cycle (within 3 days of Day 1 of each subsequent cycle) and End of Study. See **Table 7** for tests to be conducted at each time point.

^c Serum chemistry collected at Screening, Days 1, 8, 15 and 22 of Cycle 1, Day 1 of each subsequent cycle (within 3 days of Day 1 of each subsequent cycle) and End of Study. See **Table 7** for tests to be conducted at each time point.

^d Urinalysis collected at Screening, Day 1 of Cycle 1, Day 1 of each subsequent cycle (within 3 days of Day 1 of each subsequent cycle) and End of Study. See **Table 7** for tests to be conducted at each time point.

^e ECGs performed pre-dose and approximately 3 hours post-dose (following morning dose only)

^f Bone marrow aspirate required at Screening; at end of Cycles 1 and 3, every 2 cycles thereafter, and at relapse/progression, unless peripheral blood absolute count is $\geq 5.0 \times 10^9$ cells/L. See **Table 7** for tests to be conducted at each time point.

^g Disease Response Assessment may include bone marrow assessment, hematology for blood counts, physical exam, etc.

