2.2.3. Per Protocol Set (PPS) Population

For a particular measure, the per protocol set (PPS) includes those subjects in the FAS who have a valid baseline and one or more post-treatment assessments for that measure of interest.

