2.3.2. Missing Data Conventions

Unless otherwise specified, missing data will be considered missing and will not be imputed.

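### Objective response is analysed only in subjects with a post-treatment assessment, so treated subjects who leave unassessed drop out of the denominator

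*SAP*

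**What the plan says.** SAP 3.3 places all efficacy analyses, for Phase 1 by dose cohort and for Phase 2a by disease cohort, on the per-protocol set: "using the Per Protocol Population (PPS dataset"). SAP 2.2.3 defines that set, measure by measure, as FAS subjects "who have a valid baseline and one or more post-treatment assessments for that measure of interest". Protocol 8.2 gives the same definition: "the per-protocol set (PPS) includes those subjects in the FAS who have a valid baseline and one or more post-treatment assessments". The FAS itself is everyone given any study drug (SAP 2.2.1).

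On missing data, SAP 2.3.2 says that, unless otherwise specified, "missing data will be considered missing and will not be imputed". SAP 3.3.1 gives objective response within 3 cycles as the primary efficacy endpoint and has no rule for subjects without a response assessment.

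On timing, Protocol 7.2.4 states: "Disease assessments will be made at the end of Cycle 1 and Cycle 3 and every two cycles thereafter". Protocol 6.2.5 puts the first of these at Day 28 ± 3 days. Note g of Protocol Appendix D describes the content loosely: "Disease Response Assessment may include bone marrow assessment, hematology for blood counts, physical exam, etc".

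Protocol 8.3.2.1 words the endpoint this way: "The primary efficacy endpoint is the proportion of subjects treated at the MTD in each disease cohort". It does not name an analysis set. Protocol 8.3.1.1 assigns the FAS to safety only.

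**The concern.** Whether a subject enters the response denominator depends on something that happens after dosing: staying long enough to be assessed. Subjects who die or stop for toxicity in Cycle 1 are the ones most likely to be missing, and they cannot have a documented response. Leaving them out makes the drug look more active than it was among those who received it.

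The set is also loosely specified. Neither document says what makes a baseline valid, or whether a blood count or a physical examination alone counts as a response assessment. The study is unblinded (SAP 1.4.3), so the denominator could be settled once the responders are known.

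The descriptive rate and its 90% interval are all that the primary efficacy endpoint delivers, and nothing later in the plan corrects them.

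**Working it through.** **1. How a treated subject becomes unassessed.**
- The first scheduled response assessment is Day 28 ± 3, so about Day 25 to 31 (Protocol 6.2.5).
- The End of Study visit includes no disease response assessment (Protocol 6.5, Appendix D). Subjects who stop early need not attend it: "they should be encouraged to complete the end-of-study assessments" (Protocol 4.3.1).
- A response assessment is scheduled at progression (Protocol 6.4), and the investigator may add others (Protocol 7.2.4). Subjects with either of these stay in.
- Only undosed subjects are replaced (Protocol 4.3.2, SAP 1.4.4).

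The group at risk is therefore subjects who die, stop or withdraw in Cycle 1 with no progression or discretionary assessment. Protocol 1.7.2 reports a median of 2 treatment cycles (range 1–28), so short treatment is common, but it does not say how many subjects went unassessed.

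**2. The plan's own figures.** SAP 2.1 gives 8 cohorts × 6 = 48 for Phase 1, and 48 + 20 = 68 in total. Both reproduce. No response rate, precision or dropout figure is stated.

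**3. Effect on the rate.** With *r* responders, *N* treated and *k* unassessed:
- FAS, unassessed as non-responders: *r*/*N*
- PPS: *r*/(*N* − *k*)
- Ratio, for *r* ≥ 1: *N*/(*N* − *k*)

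*N* = 20 comes from SAP 2.1, taking the MDS/CMML cohort as one group. *k* and *r* are assumptions. The ratio is 20/19 = 1.05, 20/18 = 1.11 and 20/16 = 1.25 for *k* = 1, 2 and 4.

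**4. Intervals.** The 90% level is from Protocol 8.3.2.1 and SAP 4.1.4. No method is named there, so exact Clopper-Pearson is assumed: lower limit = the 0.05 quantile of Beta(*r*, *n* − *r* + 1), upper limit = the 0.95 quantile of Beta(*r* + 1, *n* − *r*). For *r* = 0 the lower limit is 0 and the upper is 1 − 0.05^(1/*n*).

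| Unassessed *k* | *n* | *r* = 4 | *r* = 2 | *r* = 0 |
|---|---|---|---|---|
| 0 | 20 | 20.0% (7.1–40.1) | 10.0% (1.8–28.3) | 0% (0–13.9) |
| 1 | 19 | 21.1% (7.5–41.9) | 10.5% (1.9–29.6) | 0% (0–14.6) |
| 2 | 18 | 22.2% (8.0–43.9) | 11.1% (2.0–31.0) | 0% (0–15.3) |
| 4 | 16 | 25.0% (9.0–48.4) | 12.5% (2.3–34.4) | 0% (0–17.1) |

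**5. Phase 1 cohorts** (3 to 6 subjects each, SAP 2.1), with one responder and one unassessed subject:
- Cohort of 3: 1/3 = 33.3% (1.7–86.5) becomes 1/2 = 50.0% (2.5–97.5).
- Cohort of 6: 1/6 = 16.7% (0.9–58.2) becomes 1/5 = 20.0% (1.0–65.7).

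**6. Comparison with the protocol's interim reporting.** Protocol 1.7.2 uses all-treated denominators for disease control: 8/25 in AML and 4 of 8 in MDS, out of 25 and 8 treated. The 3 AML partial remissions give 3/25 = 12.0% (3.4–28.2) on that basis. If 5 of the 25 had been unassessed (an assumption), the PPS rate would be 3/20 = 15.0% (4.2–34.4).

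**The case against.** The strongest reply is that the affected group is narrow and the consequence small. Progressing subjects have a scheduled assessment. If blood counts qualify, those on Days 8, 15 and 22 would bring in almost everyone. For one or two exclusions in Phase 2a, the shift is small against the interval width. The primary objective is safety on the FAS, and no hypothesis is tested (SAP 2.4.2). All of this stands and limits the severity, but the broad reading of a qualifying assessment is not written down.

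A second reply is that the response criteria already contain catch-all classes: Treatment Failure for AML and Progressive Disease for MDS/CMML (Protocol 7.2.2). Neither document applies these to an unassessed subject or says that they override the PPS filter.

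Third, the disposition table on the FAS gives the number treated, so a reader could divide responders by treated if the response table shows counts. The FAS listings would also allow this. That is true, but the reported estimate and interval would still be the PPS ones.

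Fourth, the protocol's reference to subjects treated at the MTD may only select the dose level. That is fair. The SAP set is narrower than this wording suggests, but there is no plain contradiction. Finally, the copy reviewed lacks the text between SAP 2.4.4 and 2.4.6, so the absence of a non-responder rule or an all-treated rate is established only for the visible text.

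**Conclusion.** The concern holds and should be fixed. Read together, SAP 3.3, 2.2.3 and 2.3.2 remove treated but unassessed subjects from the objective-response denominator, and the assessment that would keep a subject in is not defined. With at least one responder, the reported rate is multiplied by *N*/(*N* − *k*); with none it stays at 0% and only the upper limit rises. If every treated subject is assessed, PPS and FAS coincide and nothing changes.

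The sizes shown rest on assumed values of *k* and *r* and on exact intervals. The effect is on a descriptive estimate and its 90% interval, not on error rates or power. SAP 3.3 also places PFS and OS on the PPS; an effect on PFS is possible but has not been shown.

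**What to change.** In SAP 3.3:
- Make the FAS the main set for objective response, and count treated subjects with no post-baseline disease assessment as non-responders.
- State that PFS and OS include all FAS subjects from first dose, with every death an event. The endpoint definitions already count deaths; what needs saying is that no treated subject is filtered out.
- Keep the PPS as a sensitivity analysis, relabelled response-evaluable. Define its qualifying assessment for each measure, including whether blood counts alone are enough.
- Report the number excluded from that set, with reasons.

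The cost is one SAP paragraph and one extra set of tables, with no new data collection. The reported response rate may be slightly lower.

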3.3.1. Primary Endpoints

The primary efficacy endpoint is the proportion of subjects with objective response achieved within 3 cycles of treatment with FF-10501-01 (i.e., within 3 months) in subjects with relapsed/refractory AML or relapsed/refractory high-risk MDS or CMMML.

3.3.2. Secondary Endpoints

The proportion of subjects with MDS who have hematologic improvement in peripheral blood or bone marrow blast count at any time after initiation of treatment with FF-10501-01. Hematologic improvement in blast count is defined as $\geq 50\%$ reduction in peripheral blood or bone marrow blast count when compared with the baseline value.

Progression-Free Survival: length of time from the date of first administration of study drug to the first objective evidence of disease progression or death, whichever is earlier.

Overall Survival: length of time from the date of first administration of study drug to the date of death from any cause.

3.3.3. Exploratory/Other Analyses

Pharmacokinetic and pharmacodynamic analyses will be provided by an outside laboratory.

3.4. Analysis of Safety and Tolerability

3.4.1. Study Drug Administration

Overall duration of exposure, dose intensity, and relative dose intensity will be summarized using descriptive statistics by dose cohort for Phase 1 subjects and by MDS/CMMML disease cohort for Phase 2a subjects. Duration of exposure to study drug in each cycle will be calculated as the date of last dose minus the date of first dose plus one if there are no drug interruptions. For drug interruptions, the number of days in each cycle will be calculated as date of last dose minus the date of first dose plus one times the actual dose taken (in mg) divided by the dose prescribed (in mg) during the cycle. The number of days in all such cycles will be added within each dose cohort to calculate overall duration. The total dose taken will be calculated based on the actual dose information collected in the CRF. Dose intensity will be calculated as the total dose divided by the number of scheduled days on drug. Relative dose intensity will be calculated by dividing the dose intensity by starting dose.

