5.2. Study Drug Administration

FF-10501-01 will be provided directly from the drug distribution center designated by FPHU.

Subjects should be scheduled to begin study therapy following completion of Screening. FF-10501-01 will be administered orally at the dose level prescribed per cohort twice each

day (**approximately every 12 hours**). For subjects on the 21-day dosing schedule, treatment will be continuous for 21 days for each 28-day cycle (=1 cycle). See **Appendix A** for drug dispensing guidelines.

A sufficient supply of FF-10501-01 will be dispensed to the subject by the investigator or trained designee for the subject to take on an outpatient basis between visits.

The following instructions should be reviewed with the subject and a written copy of the instructions provided to the subject:

- Take the prescribed dose of FF-10501-01 tablets (either 50 mg or 200 mg or both) by mouth twice each day with the second dose about 12 hours after the first dose.
- Take the tablets with a full glass of water (approximately 8 ounces). Swallow the tablets whole. Tablets should be taken in the fasting state, approximately 2 hours before or 2 hours after a meal.
- Your dose may be reduced if you have side effects. If a dose reduction is required, follow the instructions given by your doctor. Do not reduce the dose unless your doctor tells you to do so.
- If a scheduled dose of study drug is missed and less than 6 hours have passed since the scheduled dosing time, immediately take the missed dose. If more than 6 hours have passed since the scheduled dosing time, do not take the missed dose. Wait and take the next regularly scheduled dose.
- Each day record the number and dosage of tablets taken on the diary card. If a dose is missed, include the reason the dose was not taken.
- Return the diary card to your study doctor at each visit.
- Return opened and unopened bottles in which the tablets were dispensed.
- Adherence with the study treatment regimen must be assessed at each visit by checking the returned drug supply and reviewing the diary card. Study drug therapy must be reported in the appropriate case report form (CRF) module.

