5.4.2. Instructions Regarding Dose Delays and Dose Modifications

Adverse events considered for treatment interruption and dose reduction will exclude the events assessed by the investigator as exclusively related to underlying disease or medical

condition/concomitant treatment. If treatment must be delayed for reasons other than toxicity, contact the Medical Monitor to discuss the reasons for delay and plans for resuming study therapy.

- Treatment may be delayed up to 14 days. If the subject has completed two cycles and, in the investigator's opinion, is receiving benefit, treatment may be delayed for longer than 14 days and then resumed following a discussion with the Medical Monitor.
- Subjects who experience a toxicity requiring reduction in dose level may continue treatment at the lower dose level until disease progression or unacceptable toxicity. Once the dose has been reduced it may not be escalated to the starting dose.
- See **Appendix B** for FF-10501-01 dose modification requirements.

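### SAP 3.4.1 can discount days twice when an interruption is not resumed within the cycle, and it adds days by cohort although its own summary needs one duration per subject

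*SAP*

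**What the plan says.** SAP 3.4.1 gives two rules for the duration of a cycle. In an undisturbed cycle it is "the date of last dose minus the date of first dose plus one if there are no drug interruptions". For drug interruptions the same elapsed time is used, but "plus one times the actual dose taken (in mg) divided by the dose prescribed (in mg) during the cycle". No brackets are printed. The section does not define an interruption, and it does not say whether the prescribed dose runs to the end of the scheduled dosing days or only to the last dose taken.

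The cycle values are then combined: "The number of days in all such cycles will be added within each dose cohort to calculate overall duration".

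The same section opens with the intended output: "Overall duration of exposure, dose intensity, and relative dose intensity will be summarized using descriptive statistics by dose cohort for Phase 1 subjects", with the MDS/CMML disease cohort taking that place for Phase 2a. The opening of SAP Section 3 says what this means: "Continuous variables will be summarized using descriptive statistics (n, mean, SD, median, minimum, and maximum").

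Dose intensity is defined separately as total dose over scheduled days on drug, and relative dose intensity as that figure over the starting dose. Neither uses the duration.

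**The concern.** Two things look wrong.

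- **Double discount.** Elapsed time from first to last dose stops at the last dose. When a hold runs past the end of the dosing period, the missed days are already outside that interval. A ratio against the full cycle's prescribed dose removes them again. Because the ratio is in milligrams, it can also convert a lower dose into fewer days, which mixes duration with intensity.
- **Wrong level of addition.** A total of days over a cohort is one number. The planned statistics need one number per subject, and no subject-level total is defined.

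The primary objective is safety and tolerability, and the exposure table is the context in which the adverse event tables are read. An understatement that falls on subjects whose dosing was held would make that context less reliable for them.

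**Working it through.** The documents state no numeric exposure figure, so there is nothing to reproduce. The rules of SAP 3.4.1 are applied below to example cycles and compared with the days on which drug was taken.

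**Inputs**
- Dosing days: Protocol 5.2, "treatment will be continuous for 21 days for each 28-day cycle".
- No-interruption rule: L − F + 1, where F and L are the days of first and last dose in the cycle.
- Interruption rule, bracketed as it must be meant: (L − F + 1) × A/P, where A is mg taken and P is mg prescribed.
- Reduced dosing: Protocol 5.4.2, "Subjects who experience a toxicity requiring reduction in dose level may continue treatment at the lower dose level"; Protocol Appendix B has steps to 75%, 50% and 25% at the 400 mg/m² level.
- Assumption for steps 1, 3 and 4: P is the full cycle's dose at the original level. This is the plainer sense of a dose prescribed during the cycle, but the SAP does not say so.

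**Step 1. Hold not resumed in the cycle; full dose on days 1 to k.**
Elapsed time is k and A/P = k/21, so the rule returns k × k/21.

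| Last dose on day | Days dosed | SAP result |
|---|---|---|
| 7 | 7 | 49/21 = 2.33 |
| 10 | 10 | 100/21 = 4.76 |
| 14 | 14 | 196/21 = 9.33 |
| 18 | 18 | 324/21 = 15.43 |

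The shortfall is k − k²/21, which is largest at k = 10.5: 10.5 − 5.25 = 5.25 days. Over a subject with one full cycle and a second with its last dose on day 10, the rule gives 21 + 4.76 = 25.76 against 31, or −5.24/31 = −17%. Two cycles is the median reported in Protocol 1.7.2.

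This pattern is foreseeable. Appendix B interrupts dosing until toxicity resolves, and Protocol 5.4.2 allows a delay of up to 14 days. A 14-day hold that begins on day 8 covers days 8 to 21, so the cycle's last dose falls on day 7.

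**Step 2. The same case on other readings.**
- P counted only to the last dose: A/P = k/k = 1, result k, which is correct.
- A permanent stop not treated as an interruption: the first rule gives k, which is correct.
- No brackets, literal order of operations: a last dose on day 10 gives 9 + 10/21 = 9.48.

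**Step 3. Gap on days 8 to 14, resumed in the cycle (14 days dosed, 21 elapsed).**
- Resumed at full dose: 21 × 14/21 = 14.00, correct. Without brackets it would be 20 + 14/21 = 20.67, so the brackets need to be printed.
- Resumed at 75%: A is worth 7 + 0.75 × 7 = 12.25 full-dose days, and 21 × 12.25/21 = 12.25 against 14 dosed.
- Resumed at 50%: 7 + 0.5 × 7 = 10.5, giving 10.50 against 14 dosed.

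**Step 4. Dependence on schedule.** Ten days of full dosing followed by an unresumed hold would be reported as 100/14 = 7.1, 100/21 = 4.8 or 100/28 = 3.6 days on the 14-, 21- or 28-day schedule, although the days on drug are the same.

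**Step 5. Level of addition.** Take an assumed cohort of three: two full cycles plus 10 days, one full cycle plus 10 days, and six full cycles. Days dosed per subject are 52, 31 and 126: mean 69.7, SD 49.9, median 52. The cohort total is 209, from which no SD, median or range can be recovered. Under the step 1 reading the values become 46.76, 25.76 and 126 (total 198.5, median 46.8).

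Two further gaps show here. The sentence on adding days names dose cohorts only, so Phase 2a disease cohorts have no stated rule. And *such cycles* could mean only the interrupted ones.

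**The case against.** The strongest reply is that the low figures need a particular reading. The documents treat interruption and permanent discontinuation as different things (SAP 3.4.2, SAP 4.3, Protocol Appendix B). A subject who stops for good on day 7 can therefore fall under the first rule and get 7 days. If the prescribed dose is counted only to the last dose, an unresumed hold also comes out right. This stands, and it rules out a broader claim that a reader might infer: that everyone who stops mid-cycle is understated. It does not remove the case of a temporary hold that runs past the cycle's dosing days. That is an interruption in the documents' own terms, and the SAP does not limit the prescribed dose to the last dose.

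On dose reduction, a reader might infer that a whole cycle at half dose is reported as 10.5 days. The text does not support that: with no interruption the first rule applies and gives 21. Appendix B also labels its reductions as adjustments for the next treatment, and if the prescribed dose is reset to the lower level, the 12.25 in step 3 does not arise. The mixing of duration with intensity therefore depends on resumption at a lower dose within an interrupted cycle, with the prescribed dose held at the original level.

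On addition, the promise of descriptive statistics shows that per-subject values are intended. This is fair: the section contradicts itself, and it does not record a decision to report cohort totals only.

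Finally, exposure duration is not a denominator for any planned rate. SAP 3.4.2 reports numbers and percentages of subjects, and SAP 1.3.2 counts DLTs per subject by Day 28. This also stands and limits the consequence.

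**Conclusion.** The point holds in a limited form. For an interruption not resumed within the cycle, with the prescribed dose taken over the full cycle, SAP 3.4.1 removes the missed days twice. On the 21-day schedule the loss is at most 5.25 days per affected cycle, and 17% in the two-cycle example. The 67% shortfall for a last dose on day 7 (2.33 against 7) is a single-cycle figure; it is a subject's overall error only if that is the subject's sole cycle. A reduction after an interruption shrinks the count further if the prescribed dose stays at the original level. A gap resumed at full dose is computed correctly, as is a permanent stop handled by the no-interruption rule.

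The conflict over addition needs none of these assumptions: days added by cohort cannot supply the statistics that the same section promises.

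A reader might infer that tolerability conclusions are biased. The documents do not support that. No hypothesis test is planned (SAP 2.4.2), and no efficacy endpoint, adverse event rate, dose intensity or relative dose intensity uses this duration. The effect is confined to the descriptive exposure table.

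**What to change.** Replace the duration sentences in SAP 3.4.1 so that they say the following:

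- Duration of exposure for a subject is the number of calendar days on which any study drug was taken, from the diary and CRF dosing records, summed over all of that subject's cycles, interrupted or not.
- These per-subject values are summarised with n, mean, SD, median, minimum and maximum, by dose cohort in Phase 1 and by disease cohort in Phase 2a.
- The ratio of actual to prescribed milligrams is dropped from duration. Dose shortfall is reported through dose intensity and relative dose intensity, as already planned.

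Defining the prescribed dose as running only to the last dose would cure the double discount, but it would leave a milligram ratio inside a count of days and would not settle the level of addition.

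The cost is a short SAP edit and the matching table programming. Protocol 5.2 already requires a daily diary, and SAP 4.3 already lists it, so no new data are needed. One small drawback is that, under twice-daily dosing, a day with one dose taken counts as a full day; the missed dose then shows in dose intensity.
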